### 9.7.3.3 Statistical Methods for Analysis of Effectiveness Variables

The simple percentage of patients achieving SVR12 will be calculated and a two-sided 95% confidence interval (CI) of the percentage based on the Wilson's Score method will be computed.

Corresponding methods will be used for other response rates (EoT response rate, relapse rate, viral breakthrough). The relapse rates will be estimated in patients of the CP analysis groups with EoT response and sufficient HCV RNA measurements post-treatment. Viral breakthrough rates will be estimated in all patients of the CP analysis groups, who have at least one undetectable HCV RNA measurement on-treatment and at least one on-treatment or EoT measurement thereafter.

Univariate and multiple logistic regression (MLR) methods will be used to investigate the impact of the following explanatory covariates on SVR12:

- Key demographic information
- Mode of CHC infection
- HCV RNA level at baseline
- Most recent stage of liver fibrosis
- HCV genotype and subtype (if available)
- Type of treating institute
- Liver and/or CHC related co-morbidities
- Key clinical chemistry and hematology laboratory variables at baseline
- In treatment experienced patients only:
  - Most recent prior treatment for CHC
  - Outcome of most recent prior CHC treatment

Further details and additional covariates will be specified in the SAP.

These analyses will be of exploratory nature, data driven, and will be repeatedly performed for the CP. Backward selection procedures will be applied to generate the final MLR models which consider only covariates for which the percentage of patients with available data is greater than 80% of the patient group analyzed. A p-value <0.05 will be used for the covariates to stay in the model in a backward elimination step. Logistic

---

Confidential Information

regression methods will also be used to investigate the impact of treatment adherence on SVR12.

#### 9.7.4 Clinical Laboratory Data

All reported clinical laboratory test results will be assigned to one of the time points using the time windows specified in the table below.

**Table 4 - Analysis Time Windows**

Phase	Time point	Time Window
Pre-Treatment	Baseline	Last value prior to start of study treatment (i.e. $\leq$ study day 1)
Treatment Weeks	4 (day 29)	Study day during treatment period (Study day 1 = first treatment day) 15 - 42
	8 (day 57)	43 - 70
	12 (day 85)	71 - 98
	16 (day 113)	99 - 126
EoT	Actual EoT	Study day of last dose (28 days prior to EoT - 14 days post EoT)
Post Treatment	4 weeks (28 days post EoT)	8 – 56 post EoT
	12 weeks (84 days post EoT)	57 – 126 post EoT
	24 weeks (168 days post EoT)	127 – 252 post EoT
	48 weeks (336 days post EoT)	253 – 420 post EoT

Mean changes from baseline to each post-baseline visit will be summarized descriptively.

Laboratory data values collected during the treatment period will be categorized as low, normal, or high based on reference ranges used in this study. The number and percent of patients who experience post-baseline shifts during treatment in clinical laboratory values

Confidential Information

No use or disclose outside AbbVie is permitted without prior written authorization from AbbVie  
Version 3.0. (22. Apr 2015) – Germany V3.0 (17. November 2016)

Page 41 of 63

from low/normal to high and high/normal to low based on the reference range will be summarized.

Additional details of the analyses of clinical laboratory data will be specified in the SAP.

### **9.7.5 Patient Questionnaires**

#### **Functional Assessment of Chronic Illness Therapy-Fatigue (FACIT-F)**

The FACIT-F Scale is written at the 4th grade-reading level as measured by the Lexile Framework, and is specifically formatted for ease of self-administration. Respondent burden takes 2-3 minutes for an average patient to complete. The FACIT-F questionnaire is presented in Annex 1.

#### **Assessment of work productivity and activity impairment – WPAI Hep C V2.0**

The WPAI questionnaire will be used to measure work absenteeism, work presenteeism, and daily activity impairment. The WPAI questionnaire was created as a patient-reported quantitative assessment of both reduced productivity at work and non-work activities. WPAI has been validated as a general health measure (WPAI-GH) and can be easily modified for specific health condition, disease or problem (WPAI-SHP). WPAI Hep C V2.0 is the HCV specific questionnaire that will be used in this study). Respondents are asked about time missed from work and time while at work during which productivity was impaired in the past seven days. Results of WPAI are expressed as a percentage of impairment from 0 to 100, with higher percentages indicating greater impairment and less productivity:

- % Presenteeism – percentage of impairment while working due to health problem
- % Absenteeism – percentage of work time missed due to health problem
- % Total work productivity impairment (TWP) – percentage of overall work impairment due to health problem
- % Total activity impairment (TAI) – percentage of general (non-work) activity impairment due to health problem

The WPAI Hep C should require approximately 5 minutes to complete and is presented in Annex 2.

### Pictorial Representation of Illness and Self-Measure (PRISM)

The burden of suffering can be evaluated by using PRISM (Pictorial Representation of Illness and Self-Measure), which is a brief quantitative method to assess the perceived burden of suffering due to illness. The PRISM tool consists of an A4-size metal board, which stands for the patient's life and a yellow disk, representing the patient, is fixed at the bottom right-hand corner. The patient is asked to reflect the importance of the illness in his/her life by placing a red disk, which represents his/her illness, on the metal board (Annex 3).

### Patient Activation Measure – (PAM-13)

PAM 13 is a measure used to assess the patient knowledge, skill, and confidence for self-management. It should require approximately 7 minutes to complete and is presented in Annex 4.

## **9.7.6 Tolerability Analysis**

All tolerability variables will be summarized using descriptive statistical methods for the SP stratified by type of combination treatment and scheduled treatment duration.

All SAEs, non-serious AEs and pregnancy occurrences are to be reported for patients included in the study (see Section 11.0 and 9.2.3). AEs will be coded using MedDRA. The number and percentage of patients with treatment-emergent AEs (i.e. any reported event that begins or worsens in severity after initiation of study drug through 30 days post-study drug dosing) will be tabulated by primary MedDRA SOC and PT. Corresponding summary tables will be provided for all serious treatment-emergent AEs. The tabulation of the number of patients with treatment-emergent AEs by severity and relationship to study drug will also be provided. Patients reporting more than one AE for a given MedDRA PT will be counted only once for that term using the most severe incident for the severity summary table and the most related for the relationship summary table. Patients reporting more than one type of event within a SOC will be counted only once for that SOC.

Additional details of the analysis of AEs will be specified in the SAP.

### **9.7.7 Interim Assessments**

Interim assessments are planned, details will be specified in the SAP.

### **9.8 Quality Control**

The sites will be instructed in the protocol, the functionality and handling of the eCRF, and the requirement to maintain source documents for each patient in the study (see Section 9.4).

A comprehensive data validation program utilizing front-end checks in the eCRF will validate the data. Automated checks for data consistency will be implemented, discrepancies need to be solved by the researcher in the eCRF before the module can be completed. Follow-up on eCRF data for medical plausibility will be done by AbbVie personnel (or their representatives). The principal investigator of each site will finally review the eCRFs for completeness and accuracy of available data and provide his or her electronic signature and date to eCRFs as evidence thereof.

Continuous monitoring of the study and frequent site telephone contacts will be done by AbbVie or a CRO working on behalf of AbbVie.

### **9.9 Limitations of the Research Methods**

The limitations of observational studies, such as uncontrolled confounding by lack of randomization, and difficulties to clearly interpret treatment effects in the context of missing data are well known. Their validity can be increased by accurate outcome measurements, documentation of the most common confounders, sufficient length of follow-up and by activities to obtain complete recording of available data as well as by searches for missing key data.

The most important outcome measure in this study is HCV RNA. Missing or unrecorded follow-up HCV RNA data can in particular lead to an underestimation of the real SVR rate as compared to the SVR rate of interventional trials. Highly sensitive and quantitative diagnostic tests are required to measure HCV RNA levels in blood. In an observational study each center will be using its own test – either commercially available or so-called “home-brew” tests – which might change from one visit to the next within a patient data set. The challenge is to accurately and consistently document test properties such as the LLoD and the ILLoQ to put the results into perspective of prior outcomes from

randomized controlled trials with (usually) central laboratory assessments for all trial participants.

## 10.0 Protection of Human Subjects

This observational study will be run in compliance with local laws and regulations (§ 4 Arzneimittelgesetz, AMG). Notification/submission to the responsible regulatory authorities, Ethics Committee (EC), Health Insurance bodies and Competent Authorities (CAs) will be done as required by local laws and regulations.

The investigator is responsible to ensure that written patient authorization to use and/or disclose patients' pseudonymized health data will be obtained prior to patient inclusion.

To maintain patient confidentiality, no demographic data that can identify the patient will be collected (e.g. initials, date of birth) - only the patient age will be collected. In order to protect patient identity, a unique number will be assigned to each patient and related study recording.

## 11.0 Management and Reporting of Adverse Events/Adverse Reactions

PRO data are not considered a potential source of adverse reactions. However, participating sites should review the PRO data and if a possible product-related event (including a suspected adverse reaction) is noted, the HCP must determine whether the event is related to the ABBVIE REGIMEN ± RBV (or any other AbbVie authorized product) and if so, it should be reported to AbbVie.

Medication errors (this refers to any unintentional error in the prescribing, dispensing, or administration of a medicinal product while in control of the HCP, patient or consumer) should be reported by the HCP to AbbVie.

The relevant AbbVie Pharmacovigilance contact details are specified below:

Name: Dr. [REDACTED]

Address: [name]

Tel.: [REDACTED]

Fax: [REDACTED]

---

Confidential Information

## 11.1 Adverse Event Definition and Serious Adverse Event Categories

An adverse event (AE) is defined as any untoward medical occurrence in a patient, which does not necessarily have a causal relationship with their treatment. An AE can therefore be any unfavorable and unintended sign (including an abnormal laboratory finding), symptom, or disease temporally associated with the use of a medicinal product, whether or not the event is considered causally related to the use of the product.

Such an event can result from use of the drug as stipulated in the labeling, as well as from accidental or intentional overdose, drug abuse, or drug withdrawal. Any worsening of a pre-existing condition or illness is considered an AE.

If an AE meets any of the following criteria, it is considered a serious adverse event (SAE):

Death of Patient:	An event that results in the death of a patient.
Life-Threatening:	An event that, in the opinion of the investigator, would have resulted in immediate fatality if medical intervention had not been taken. This does not include an event that would have been fatal if it had occurred in a more severe form.
Hospitalization:	An event that results in an admission to the hospital for any length of time. This does not include an emergency room visit or admission to an outpatient facility.
Prolongation of Hospitalization:	An event that occurs while the study patient is hospitalized and prolongs the patient's hospital stay.
Congenital Anomaly:	An anomaly detected at or after birth, or any anomaly that results in fetal loss.
Persistent or Significant Disability/Incapacity:	An event that results in a condition that substantially interferes with the activities of daily living of a study patient. Disability is not intended to include experiences of relatively minor medical significance such as headache, nausea, vomiting, diarrhea, influenza, and accidental trauma (e.g. sprained

---

Confidential Information

ankle).

**Important Medical Event  
Requiring Medical or  
Surgical Intervention to  
Prevent Serious Outcome:**

An important medical event that may not be immediately life-threatening or result in death or hospitalization, but based on medical judgment may jeopardize the patient and may require medical or surgical intervention to prevent any of the outcomes listed above (i.e. death of patient, life threatening, hospitalization, prolongation of hospitalization, congenital anomaly, or persistent or significant disability/incapacity). Additionally, any elective or spontaneous abortion or stillbirth is considered an important medical event. Examples of such events include allergic bronchospasm requiring intensive treatment in an emergency room or at home, blood dyscrasias or convulsions that do not result in inpatient hospitalization, or the development of drug dependency or drug abuse.

## 11.2 Severity

The following definitions will be used to rate the severity for any AE being collected as an endpoint/data point in the study and for all SAEs.

- Mild:** The AE is transient and easily tolerated by the patient.
- Moderate:** The AE causes the patient discomfort and interrupts the patient's usual activities.
- Severe:** The AE causes considerable interference with the patient's usual activities and may be incapacitating or life threatening.

## 11.3 Relationship to Pharmaceutical Product

The following definitions will be used to assess the relationship of the AE to the use of product:

- Reasonable Possibility** An AE where there is evidence to suggest a causal relationship between the product and the AE.

---

Confidential Information

**No Reasonable Possibility** An AE where there is no evidence to suggest a causal relationship between the product and the AE.

If no reasonable possibility of being related to product is given, an alternate etiology must be provided for the AE.

#### 11.4 Serious Adverse Event Collection Period

SAEs will be reported to AbbVie from the time the physician obtains the patient's authorization to use and disclose information until 30 days or 5 half-lives following the intake of the last dose of physician-prescribed treatment.

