**Table 2 - Data Documentation Schedule**

Assessment/ Procedure (only available data to be collected; no diagnostic or monitoring procedures to be applied to the patients apart from those of routine clinical practice)	Baseline	Treatment Period			Post-treatment (PT) Period			
		On-treatment visits	Mid treatment visit for pts receiving 24 weeks of therapy	EoT b	Early PT visit	SVR 12 visit	SVR 24 visit	SVR 48 visit
Patient authorization	X a							
Demographic information	X							
IL28B	X							
Relevant CHC disease characteristics	X							
Liver fibrosis stage	X					X		X
CHC treatment history	X							
HCV genotype and subtype	X							
HCV RNA samples	X	X	X	X	X	X	X	X
Clinical chemistry and hematology	X	X	X	X	X	X	X	X
ABBVIE REGIMEN initiation documentation	X							
ABBVIE REGIMEN adherence		X	X	X				
Concomitant medication	X	X	X	X				
Relevant medical history, co-morbidities	X							
sAE, AE and pregnancy reporting	X	X	X	X	X c	X d	X d	X d
For patients receiving RBV: Evidence, in accordance with local label, that female patient or female partner of male patient is not pregnant	X							
Patient questionnaires: FACIT-F	X	X	X	X		X		X
Patient questionnaire: WPAI	X			X		X	X	
Patient questionnaire: PRISM	X					X		X
Patient questionnaires: PAM-13	X			X				
Patient questionnaire: PSP e (U f )			X		X			
Patient questionnaire: PSP e (U f & S g )		X		X		X		

Abbreviations: EoT = End of Treatment (at Week 12 or 24 or at premature discontinuation),  
PT = Post-Treatment

- a Written patient authorization must be obtained before any data documentation in the eCRF
- b Patients who prematurely discontinue should return to the site to document EoT data
- c Tolerability documentation until PT week 4
- d Pregnancy reporting for patients treated with DAA plus RBV
- e applicable for patients enrolled in the PSP
- f Utilization
- g Satisfaction

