#### 11.6 Pregnancy Reporting

Patients and their partners should avoid pregnancy and males should avoid sperm donation throughout the course of the HCV treatment and for 30 days after the end of treatment with DAAs only, or for 7 months after the last dose of RBV (or per local RBV label) and/or consistent with local treatment guidelines for RBV.

In the event of a pregnancy occurrence in the patient, the physician will report to AbbVie within 24 hours of the physician becoming aware of the pregnancy by using the eCRF system or notifying the AbbVie contact person identified in Section 11.0.

---

Confidential Information

The investigator is encouraged to report the pregnancy information to the voluntary RBV Pregnancy Registry, if RBV is included within the regimen.

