#### **4.2.8.3 Adverse Events**

All tolerability variables will be summarized using descriptive statistical methods for the SP stratified by treatment regimen and cirrhosis status and overall.

AEs will be coded using MedDRA. A glossary will show the verbatim terms and the corresponding coded terms used (see Table 13).

The number and percentage of patients with treatment-emergent AEs (i.e. any reported event that begins or worsens in severity after initiation of study drug through 30 days post-study drug dosing including those who are related to the study drug independent of the occurrence and those where the date of onset is missing) will be tabulated by primary MedDRA SOC and PT.

Corresponding summary tables will be provided for all serious treatment-emergent AEs and additional for all non-serious treatment-emergent AEs. In the table of non-serious AEs (that must exclude any SAE) only preferred terms that occurred at a frequency of  $\geq 5\%$  in any treatment group will be displayed (no SOCs will be displayed).

The tabulation of the number of patients with treatment-emergent AEs by severity (AEs by severity [mild, moderate, severe], AEs leading to death, AEs leading to hospitalization) and relationship to study drug will also be provided (ABBVIE regimen, ribavirin, medication error -

paritaprevir/r-ombitasvir, medication error – dasabuvir, ABBVIE regimen withdrawn, ribavirin withdrawn).

Patients reporting more than one AE for a given MedDRA PT will be counted only once for that term using the most severe incident for the severity summary table and the most related for the relationship summary table. Patients reporting more than one type of event within a SOC will be counted only once for that SOC.

The frequency of pregnancies will be displayed as well.

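### Required SAE reporting closes before any term birth conceived on or after treatment start, and no document asks for pregnancy outcomes, so congenital anomalies found at birth and late losses are not systematically captured

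*Protocol*

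**What the plan says.** Protocol 11.1 includes congenital anomaly among the SAE categories and describes it as "An anomaly detected at or after birth, or any anomaly that results in fetal loss". Under the important-medical-event category it adds that "any elective or spontaneous abortion or stillbirth is considered an important medical event".

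Protocol 11.4 requires SAEs to be reported from patient authorization "until 30 days or 5 half-lives following the intake of the last dose of physician-prescribed treatment". It makes no exception for pregnancy, gives no half-life, and does not say which of the two limits governs. In Protocol Table 2, footnote c to the early post-treatment visit reads "Tolerability documentation until PT week 4".

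Pregnancy has its own track. Footnote d of Table 2 puts "Pregnancy reporting for patients treated with DAA plus RBV" at the SVR12, SVR24 and SVR48 visits. Protocol 11.6 asks patients and partners to avoid pregnancy for 30 days after DAA-only treatment "or for 7 months after the last dose of RBV" (or per the local label). It requires a pregnancy in the patient to be reported within 24 hours of awareness, and it encourages, without requiring, reporting to a ribavirin pregnancy registry. The secondary variable in Protocol 9.3.2 is likewise the occurrence of pregnancy.

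On output, SAP 4.2.8.3 says "The frequency of pregnancies will be displayed as well". SAP Table 12 puts pregnancy in one table with medication errors and names no table or listing of pregnancy outcomes.

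**The concern.** A congenital anomaly is usually recognised at birth, months after conception. A protocol that makes it an SAE and then ends required SAE reporting about a month after the last dose has defined a category that its own collection rule leaves largely empty. The pregnancy track runs much longer, but as written it asks only whether a pregnancy occurred.

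Tolerability is a secondary objective, and the eligibility criteria single out ribavirin's contraception requirements and its contraindication in pregnancy. If the SAE tables show no anomalies and no late losses, a reader cannot tell whether none happened or none had to be reported.

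**Working it through.** **Inputs from the documents**
- Treatment of 12 or 24 weeks, then 48 weeks of observation (Protocol 9.2.2). The stated totals reproduce: 12 + 48 = 60 weeks and 24 + 48 = 72 weeks.
- SAE reporting limit: 30 days after the last dose (Protocol 11.4, first limb).
- Ribavirin pregnancy-avoidance period: 7 months × 30.44 days ≈ 213 days (Protocol 11.6).
- Nominal end of post-treatment observation: 48 × 7 = 336 days.

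**Assumption.** The documents give no gestation length. I take 266 days from conception to term birth, range 259 to 280, and 196 days for a very preterm birth.

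**Step 1: longest time from conception to the close of SAE reporting.** Take conception on day 1, the earliest case for a conception on or after treatment start. For ribavirin patients Table 2 asks for evidence at baseline that the patient or female partner is not pregnant.
- 12-week course: 84 + 30 = 114 days (16.3 weeks).
- 24-week course: 168 + 30 = 198 days (28.3 weeks).

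Both are below 259 days, so no term birth is covered. A very preterm birth at 196 days just fits on the 24-week course (196 < 198) but not on the 12-week course (196 > 114). A loss before day 114 or day 198, respectively, fits.

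**Step 2: conception at the last dose.** A term birth comes 266 − 30 = 236 days after close (range 259 − 30 = 229 to 280 − 30 = 250).

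**Step 3: conceptions in the ribavirin avoidance period.** 213 − 30 = 183 of the 213 days lie after close. For those conceptions every outcome, early loss included, falls outside required SAE reporting.

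**Step 4: could the 5-half-lives limb rescue this?** Half-life needed = (days from last dose to birth) / 5, with a 266-day gestation:
- conception on day 1, 24-week course: (266 − 168) / 5 = 19.6 days;
- conception on day 1, 12-week course: (266 − 84) / 5 = 36.4 days;
- conception at the last dose: 266 / 5 = 53.2 days (range 51.8 to 56.0).

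No half-life is given, so this limb cannot be shown to reach a term birth. A shorter half-life would be enough to reach some losses.

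**Step 5: what the existing visits could reach.** A term birth falls by day 336 if conception was no later than day 336 − 266 = 70 after the last dose (range 336 − 280 = 56 to 336 − 259 = 77). For conception at the end of the avoidance period, birth would come at about day 213 + 266 = 479 (68.4 weeks), beyond the planned observation.

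**Step 6: from collection to output.** SAP 4.2.8.3 counts events related to study drug as treatment-emergent whatever their date, so a late related anomaly would be tabulated if it reached the database. Nothing in Protocol 11.4 or 11.6 requires it to.

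**The case against.** The strongest reply is that the plan captures more than a bare count. Abortion and stillbirth are SAEs, and a loss of an on-treatment conception before the close would appear in the serious-event table and the SAE listing. Protocol 9.4.1.3 refers SAEs to 11.4 and pregnancies to 11.6, so the 30-day limit does not shut the pregnancy track, which runs to SVR48 in ribavirin patients. Protocol 11.5 sets a 24-hour SAE duty without an end date, the SAP keeps related events regardless of timing, and investigators are pointed to a pregnancy registry. The pregnancy table layout sits in SAP Part II and the eCRF page is not shown, so either might hold an outcome item. No objective concerns embryo-fetal safety, and few pregnancies are expected.

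Much of this stands, and it rules out three stronger readings that a reader might infer:
- That ribavirin pregnancy harm is reported with no outcomes at all. Losses inside the 114- or 198-day span are reportable SAEs.
- That no birth can occur inside the window. A very preterm birth on the 24-week course could.
- That late outcomes are barred. They are simply not required.

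It does not remove the point. Protocol 11.5 sets the speed of reporting, not the collection period, which is the subject of 11.4. The registry is voluntary and outside the study dataset. The SAP can tabulate only what sites send in. An outcome item in an unseen form or table shell would help, but neither the protocol nor the SAP text calls for one.

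**Conclusion.** The point holds in this limited form. Protocol 11.1 defines SAE categories that 11.4 closes off before any term birth conceived on or after treatment start. The longer pregnancy track has no stated outcome item, and the SAP names only a frequency. Congenital anomalies found at birth, and losses after the close, are not systematically captured, so their absence from the SAE tables would not be informative.

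The size in time is clear: at most 114 or 198 days of cover after a conception on treatment, against an assumed 259 to 280 days to a term birth. The size in patients is small. The documents give no expected number of pregnancies, and the primary SVR12 analysis is untouched. This is a minor safety-reporting correction.

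The conclusion rests on the assumed gestation length and on the 30-day limb. The 5-half-lives limb is unresolved because neither a half-life nor a rule for choosing is stated. It makes no judgement on contraception or treatment rules.

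**What to change.** Reconcile Protocol 11.1, 11.4, 11.6 and Table 2 with SAP 4.2.8.3 on data capture:

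1. In Protocol 11.4, state that pregnancy-related SAEs (congenital anomaly, fetal loss, abortion, stillbirth) are reportable up to the last study visit, and say which of the two existing limits governs other SAEs.
2. In Protocol 11.6 and Table 2, record the outcome of each reported pregnancy, if known, at the existing SVR12, SVR24 and SVR48 visits.
3. In SAP 4.2.8.3, add a listing of each pregnancy: regimen, timing relative to the last DAA and last ribavirin dose, and outcome, with a category for outcomes unknown at study end.
4. State whether partner pregnancies are covered. Protocol 11.6 asks partners to avoid pregnancy and Table 2 covers female partners at baseline, but the reporting duty names only pregnancy in the patient.

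Cost: some protocol wording, an outcome entry at visits that already exist, one SAP listing and, given the small numbers, a few extra entries. The patient authorization (Protocol 9.2.1) covers the patient's own health data, so its reach over newborn outcomes needs checking. The fix is partial: term outcomes of conceptions after about day 56 to 77 post-treatment would still be unknown at week 48, and the listing should show them as such.
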